## 5. METHODS

## 5.1 Study parameters/endpoints

### 5.1.1 Main study parameter/endpoint

Main parameter is number of CAL patients with deviating perioperative risk factors.

### 5.1.2 Secondary study parameters

Secondary parameters are number of deviating risk factors in total and feasibility of scoring a checklist during surgery.

## 5.2 Leakage Check procedure

For this study a colorectal checklist has been designed, that will be scored during surgery prior to the creation of an anastomosis. The checklist is carried out digitally on [www.naadlekkage.nl](http://www.naadlekkage.nl), so it can be completed during the surgery. The checklist contains four main general topics; general condition, perfusion, contamination and visibility of the surgical field and surgery related factors. For each topic a number of parameters and inquiries are required to be answered. A systematic review was performed summarizing the preceding studies on (perioperative) risk factors. All the parameters and inquiries (see **table 2**) for the Leakage Check procedure have been found relevant factors with proven predictive values for the occurrence of an anastomotic leakage.

*Intraoperative modifiable risk factors of colorectal anastomotic leakage.*

*A systematic review of literature*

[name]/[name]/[name]/[name]/[name]/[name]/[name]/[name]

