### **Leakage Check procedure**

The Leakage Check procedure will monitor possible perioperative risk factors right before the creation of the anastomosis. If perioperative risk factors are identified in the observational study, a follow up study will be done with a renewed Leakage Check procedure. The detected deviating risk factors will then be optimized to hopefully improve the healing of an anastomosis. At this moment no specific protocol exists whether to decide perioperatively to construct an anastomosis or to apply a stoma. A perioperative Leakage Check procedure will possibly create uniformity and increases awareness amongst surgeons and anesthesiologists in their approach to perform an anastomosis. Using a Leakage Check procedure, the actual performance status of the patient will be identified more securely.

The final purpose of this study is to assess reduction of CAL. Awareness to CAL throughout the entire treatment process needs to be extended.

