In every participating hospital one individual has been designated to determine which patients are included. Every week scheduled patients for colorectal surgery with anastomosis will be selected by one local colorectal surgeon in the VUMC and MMC. Hopefully almost all operations with anastomosis will be enrolled in our study, since there is no difference in treatment or potential damage. This must also be communicated to one main individual in the VUMC ([name]) to create a good overview of the scheduled Leakage Check procedure. The performing surgeon requests to apply the questionnaire at the moment before constructing the anastomosis. The anesthetist, operating room nurses and other relevant team members in the operating room (OR) will be asked to participate in this procedure. The questionnaire is found on the website [www.naadlekkage.nl](http://www.naadlekkage.nl). Every participating hospital has an own account on this website. Data following this procedure will be securely collected in a prospective online database. Patient characteristics, laboratory, pathologic, radiologic, hemodynamic and surgery related items will be scored and added. In order to obtain reliability of the results, the Leakage Check procedures that have been completed in more than 90% will only be taken into account.

Before starting with the execution of the Leakage Check procedure, the research will be announced to all predicted partici employees.

Important preoperative factors as well as postoperative complications need to be monitored. For every Leak Check patient, it is necessary to fill in a two pages' questionnaire with preoperative and postoperative outcome information. It is important that all CAL cases are diagnosed in accordance with the guidelines. It is necessary to comply with the definition of Reisinger in order to be reckoned as CAL. The definition of anastomotic leakage is: "Clinically relevant anastomotic leakage was defined as extraluminal presence of contrast fluid on contrast-enhanced CT scans and/or leakage when relaparotomy was performed, requiring reintervention. Indications for CT or relaparotomy were based on clinical presentation, including fever, tachycardia, tachypnea, low saturation, low urinary production, abdominal pain, and signs of ileus or gastric retention."

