Statistics are used to calculate a possible difference between patient outcomes and deviations in perioperative parameters, by means of a chi-squared test. The patients are divided into two groups, with and without CAL complication. The final purpose of this study is to optimize the risk factors in a follow up study. The determined perioperative risk factors will be ascribed optimum values by using the results of the Leak Check-Study. Dividing the patients into leaking and non-leaking groups to determine the most average values for perioperative factors. These results can be compared with the so-called optimal values from the literature of the systematic review. From these results, a new Leakage Check questionnaire will be designed for in the follow up study, containing often aberrant and modifiable perioperative factors and their optimal range. It depends on the obtained results how the optimization will take place.

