**Table 2. Leakage Check procedure**

General condition	Perfusion	Contamination and visibility	Surgery related factors
Temperature	Blood loss		Analgesia
Glucose	O 2 saturation	Contamination surgical field	Surgeon Fit to perform
Antibiotics	MAP		Elective operation Anastomose
Inotropic	Subjective rate of local perfusion		Operation Intra operative event\
Door movements	Fluid balance		Stoma Hospital

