## **6. STATISTICAL ANALYSIS**

### **6.1 Statistical plan**

Evaluation of relationships between parameters deviations and leakage rates of anastomosis. Analyses for outcome will be performed on the 2 groups, one with CAL and a group without CAL. Data will be analyzed with Statistical Package for the Social Sciences software version 20 (SPSS Inc., Chicago, IK, USA).

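### Blood loss, fluid balance and door movements would naturally build up until a check with no recorded elapsed time, so an unadjusted chi-squared test can confuse them with time to the check

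*Protocol*

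**What the plan says.** The Introduction, under the heading on the Leakage Check procedure, fixes when the check is done: "The Leakage Check procedure will monitor possible perioperative risk factors right before the creation of the anastomosis". Section 5.2 repeats that the checklist is one "that will be scored during surgery prior to the creation of an anastomosis". Both anchor the measurement to a step of the operation. Neither gives a clock time or a time since incision.

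Table 2 lists the items. Some are readings at one moment, such as temperature, MAP and oxygen saturation. Three would normally build up during surgery: blood loss and "Fluid balance" under Perfusion, and "Door movements" under General condition. The table gives them as bare labels, without unit, cut-off or time window. It lists no operating time, time since incision or time of the check, and the rest of the protocol names none.

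On analysis, Section 3 relates outcome to "deviations in perioperative parameters, by means of a chi-squared test". Section 6.1 adds: "Analyses for outcome will be performed on the 2 groups, one with CAL and a group without CAL". No covariate or stratification factor appears in either place. Section 3 then uses the leaking and non-leaking groups to derive optimum values and to design the checklist for the follow-up study.

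**The concern.** Section 4.2 admits patients with any type of anastomosis, and Section 3 reports seventeen participating hospitals, so the time from incision to check will differ between patients. An item that grows with time will be high partly because the check came late. If late checks also go with more leakage, the item is associated with CAL even when the bleeding rate, fluid rate or door traffic has no effect of its own. Adjusting for operation type alone would not remove this, because time still varies within a type.

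The stake is the primary objective, which is to find factors that are both relevant and modifiable. A total that mainly marks a long operation could be carried into the follow-up checklist as something to optimise, with a threshold that does not suit operations of another length. Unless time to the check is recorded, the study cannot tell the two explanations apart.

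**Working it through.** The protocol states no figure for duration or for its relation to CAL, so there is nothing of its own to reproduce here. The size has to come from simulation.

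**Inputs from the protocol.** 2000 patients (Section 4.1). 8% CAL, the lower end of the 8-13% incidence in the Introduction. Significance level 0.05 (Section 4.4). Uncorrected chi-squared test on a 2x2 table.

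**Assumptions.** Median time to check T of 2 h, log-SD 0.35. Hourly rate log-normal and independent of CAL, log-SD 0.3, 0.5 or 0.8. Top 30% of totals called deviating. Odds ratio (OR) for CAL of 1.0 to 1.5 per SD of log time.

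**Model.** log T = log 2 + 0.35 z, with z standard normal; logit P(CAL) = a + log(OR) × z; total = rate × T. The item has no effect on CAL.

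**Step 1: how strongly the total tracks time.** The correlation of log total with log T is 0.35 / √(0.35² + s²), where s is the log-SD of the rate:

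- s = 0.3: 0.35 / √0.2125 = 0.76
- s = 0.5: 0.35 / √0.3725 = 0.57
- s = 0.8: 0.35 / √0.7625 = 0.40

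**Step 2: how often the item without effect is declared a risk factor** (1500 simulated studies per setting):

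| OR per SD of log time | s = 0.3 | s = 0.5 | s = 0.8 |
|---|---|---|---|
| 1.2 | 26% | 17% | 10% |
| 1.3 | 51% | 31% | 18% |
| 1.5 | 85% | 62% | 35% |

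At OR 1.0 the rate is about 5%. Allowing for repeat runs, the ranges are 10-29%, 17-51% and 35-85%. A separate simulation with an upper-quartile cut, log-SD of time 0.4 and rate log-SD 0.3 to 1.0 gave about 5% at OR 1.0, then 13-26%, 15-45% and 27-81%. The median spurious odds ratios at OR 1.2 to 1.5 were 1.1 to 1.7.

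**Step 3: would an hourly rate cure it?** When the total is exactly proportional to time, dividing by T brings rejection back to 4-6%, but the model makes that certain. Suppose instead that the total does not depend on time, for example because the loss occurs in one step. Then log(total / T) has correlation −0.35 / √(0.35² + s²) with log T, where s is now the log-SD of the total: −0.76, −0.57 and −0.40. The raw total now rejects in 4-6% of studies. The hourly rate rejects falsely in about 9-81% across OR 1.2 to 1.5, and the item appears protective (odds ratios 0.60-0.88 in one set of runs). If the total grows with the square root of time, the two correlations are equal in size and opposite in sign (0.175 / √(0.175² + s²) = 0.50, 0.33, 0.21). Both analyses are then inflated: at OR 1.5, 14-50% for the total and 12-44% for the rate.

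**Step 4: keeping the total and adjusting.** A logistic model of CAL on the deviating item with log T as a covariate rejected in about 2-7% of studies in every setting run, whether the total was proportional to time, to its square root, or unrelated to it.

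**The case against.** Table 2 gives only labels. That the three items are recorded as running totals is an inference, and door movements could be a rate or a count over a fixed window. The online questionnaire, which is not shown, would settle this. Section 3 also says that "Patient characteristics, laboratory, pathologic, radiologic, hemodynamic and surgery related items will be scored and added", and operating time may be among those items. Covariates are often left to a statistical analysis plan, and none is at hand. The inflation needs duration to be associated with CAL; without that association rejection stays near 5%. Finally, the accumulated amount at the moment of anastomosis may itself be the relevant exposure for blood loss and fluid balance, and a total that marks long operations is still a valid predictor for the high-risk profile in the secondary objectives.

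Much of this stands. A reader might infer that the protocol records raw totals, that long operations do make these items false risk factors, and that hourly rates are the cure. The document supports none of the three: it does not define the items, it gives no link between duration and CAL, and the rate analysis can produce an error of the same size in the opposite direction.

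What does not stand is that this is merely missing detail. The protocol itself ties the check to a surgical step, names an unadjusted test, and uses the results to set values for the follow-up checklist. Total operating time, if collected, would still not be the time to the check.

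**Conclusion.** The point holds as conditional confounding by time to the check, and the remedy is a cheap improvement. As written, the analysis cannot separate an effect of blood loss, fluid balance or door movements from the effect of a late check. If duration is unrelated to CAL, no harm follows. If the odds ratio per SD of log time is 1.2 to 1.5, an item with no effect is flagged in roughly 10% to 85% of studies instead of 5%. That range rests on assumed values for the spread of time and rate, on a 30% cut, and on totals proportional to time. It is smaller if totals grow more slowly, and absent if they do not grow with time at all.

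**What to change.** Record the incision time and the check time as explicit fields. A website time stamp should not be relied on: the protocol mentions none, and Section 3 offers centres two ways of processing the data.

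In Sections 3 and 6.1, keep the chi-squared test. For these three items, report beside it a logistic model of CAL on the deviating item with log time from incision to check as a covariate. Report elapsed time to the check as a candidate factor in its own right. State for each item whether it is a total or a rate, and over what window.

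Do not replace the totals for blood loss and fluid balance by hourly rates. An hourly rate may be added for door movements.

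The cost is one or two data fields and a short addition to the analysis text. The statistical downside is that, if bleeding itself prolongs surgery, adjustment may remove part of a real effect. The unadjusted and adjusted results should therefore be shown together.

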**Table 2. Leakage Check procedure**

General condition	Perfusion	Contamination and visibility	Surgery related factors
Temperature	Blood loss		Analgesia
Glucose	O 2 saturation	Contamination surgical field	Surgeon Fit to perform
Antibiotics	MAP		Elective operation Anastomose
Inotropic	Subjective rate of local perfusion		Operation Intra operative event\
Door movements	Fluid balance		Stoma Hospital

### **5.3 Withdrawal of individual subjects**

Only applicable if participants decide to withdraw before surgery. The investigator can decide to withdraw a subject from the study if the patient ends up not receiving an anastomosis.

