### **Secondary Objectives:**

2. Observe deviations of the parameters in the checklist during surgery.
3. Determine the extent of these parameters as risk factors of CAL.
4. Perceiving a possible reduction of CAL due to extra emphasizing of the hemodynamic factors.
5. Creating a profile identifying high risk patients perioperatively.
6. Increasing the awareness amongst surgeons of the influence of perioperative parameter changes for CAL.

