### 3. STUDY DESIGN

The Leakage Check procedure will use perioperative risk factors identified in a systematic review. The Leakage Check procedure will be developed in a format that is already accepted and applied in the operating room before the start of the operation. Preoperative risk factors will be screened prior to the operation. This will be done by using the colon leakage score. Informed consent is requested prior to the operation.

The Leakage Check procedure is a multifactorial checklist that is scored with the whole surgical team prior to a surgical procedure. For this study a colorectal checklist has been designed, that will be scored during surgery prior to the creation of an anastomosis. The checklist is carried out by a member of the operation team. The checklist will also be offered through a website to minimize the registration burden in other hospitals. The checklist contains five main general topics; general condition, perfusion, contamination and visibility of the surgical field and surgery related factors. For each topic a number of parameters and inquiries are required to be answered.

This study is a multicentre observational cohort study with gradual introduction of the protocol (see Table 1) over the participating hospitals. At the moment there is participation of seventeen hospitals in the Netherlands. The reason being that there is a large group of anastomotic procedure outcomes without perioperative monitoring necessary that can be used to compare the Leakage Check procedure results with. To test the hypothesis, that even only keeping track of the risk factors a reduction of CAL occurs, a prospective group without perioperative monitoring is required as zero group. January 2016 is the starting point (T0) of the first hospital with the Leakage Check procedure, three months later the second hospital starts with implementing the Leakage Check procedure.

Table 1. Gradual introduction. **T**: number of months from start point till implementing a Leakage Check procedure . **Green columns**: Using a Leakage Check. **Red columns**: Not using a Leakage Check.

MMC T:0	
VUMC	T:3
To be determined	T:6
To be determined	T:9
To be determined	

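### Discretionary withdrawal of patients who end up without an anastomosis hides any diversion to a stoma, so lower leakage under monitoring could not be told apart from selection

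*Protocol*

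**What the plan says.** Section 5.3 (Withdrawal of individual subjects) has two sentences. The first reads "Only applicable if participants decide to withdraw before surgery". The second reads "The investigator can decide to withdraw a subject from the study if the patient ends up not receiving an anastomosis". The second is optional, is left to the investigator, and comes without a rule for recording or counting the patients concerned.

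Section 3 describes a checklist "that will be scored during surgery prior to the creation of an anastomosis", and adds: "The performing surgeon requests to apply the questionnaire at the moment before constructing the anastomosis". On the choice between anastomosis and stoma, the Introduction (Leakage Check procedure) says: "At this moment no specific protocol exists whether to decide perioperatively to construct an anastomosis or to apply a stoma". It continues: "A perioperative Leakage Check procedure will possibly create uniformity and increases awareness amongst surgeons and anesthesiologists in their approach to perform an anastomosis".

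Secondary objective 4 is "Perceiving a possible reduction of CAL due to extra emphasizing of the hemodynamic factors". For the matching hypothesis, Section 3 says that "a prospective group without perioperative monitoring is required as zero group", obtained by introducing the checklist hospital by hospital. The protocol does not say how patients who end up without an anastomosis are handled in that group.

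**The concern.** Patients are selected from the weekly list of those scheduled for surgery with an anastomosis, and they consent before the operation. Entry therefore rests on a planned anastomosis, whereas staying in the study can depend on whether one was made. That second event is settled during the same operation as the checklist, and the protocol itself allows that the checklist may affect it. Retention is also decided case by case, with seventeen hospitals participating and no common rule.

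The comparison at stake is monitored against unmonitored patients. Suppose that teams using the checklist make fewer anastomoses in patients with poor values. Leakage among the anastomoses that remain would then be lower even if healing were unchanged. To recognise this, one needs the share of planned anastomoses not made in each period, and discretionary withdrawal can remove exactly that count.

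**Working it through.** The protocol gives no figure on this point, so there is none to reproduce. The calculation below shows only what selection could do.

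**Inputs**
- b = 8%, baseline CAL rate: the lower end of the 8% to 13% incidence in the Summary and Introduction.
- f, the extra share of planned anastomoses not made in the monitored period compared with the zero group: assumed 5% or 10%. The protocol gives no value.
- r, the leak risk those patients would have had with an anastomosis: assumed 15% or 20%. The protocol gives no value.
- Healing is unchanged in everyone else.

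**Formulas**
- CAL per constructed anastomosis = (b − f·r)/(1 − f).
- CAL per planned anastomosis, with diverted patients kept as non-leaks = b − f·r.

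| f | r | Per constructed | Relative fall | Per planned | Relative fall |
|---|---|---|---|---|---|
| 5% | 15% | 0.0725/0.95 = 7.63% | 5% | 7.25% | 9% |
| 5% | 20% | 0.0700/0.95 = 7.37% | 8% | 7.00% | 12.5% |
| 10% | 15% | 0.0650/0.90 = 7.22% | 10% | 6.50% | 19% |
| 10% | 20% | 0.0600/0.90 = 6.67% | 17% | 6.00% | 25% |

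**No risk-related diversion.** With r = b = 8% and f = 5%, the rate per constructed anastomosis is (0.08 − 0.004)/0.95 = 8.00%, so nothing changes.

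**Higher baseline.** With b = 13% and r = 20%, the rate per constructed anastomosis is (0.13 − 0.01)/0.95 = 12.63% at f = 5% and (0.13 − 0.02)/0.90 = 12.22% at f = 10%. The relative falls are 3% and 6%.

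**What follows**
1. The rate per constructed anastomosis is the same whether diverted patients are withdrawn or kept on record as not at risk. Diversion moves the rate; withdrawal only removes the evidence of it.
2. Counting diverted patients as non-leaks lowers the rate further, so CAL per planned anastomosis does not cure the problem.
3. Without f by period, a fall of this kind cannot be separated from better healing. With f known, a reader can work out how high r would have to be for diversion alone to explain the fall, and judge whether that is credible.

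**The case against.** The strongest reply is that the rule removes nobody at risk. Sections 4.1 and 4.2 define the population as surgery with an anastomosis, Section 6.1 concerns leakage rates of anastomoses, and a patient without one has no such outcome. This stands. A reader might infer from section 5.3 that withdrawal itself brings the leak rate down. It does not.

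A second reply is that nothing shows diversion happening. The Summary says there is no intervention, Section 3 foresees no difference in treatment, and section 7.1 says participants are treated similarly. Table 2 shows no score, cut-off or rule for choosing a stoma, and the Introduction concedes that optimal values are hardly known. The moment at which a stoma is chosen is not stated either; if it comes before the checklist, the checklist cannot have caused it and its values may not exist. This also stands against any claim that the highest-risk patients do leave or that leakage does fall. It does not rule the mechanism out: the Introduction says the checklist may affect the approach to an anastomosis, objective 6 aims at surgeons' awareness, and section 7.3 speaks of extra attention to the patient's condition.

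A third tempting reading is that losing these patients attenuates the associations between checklist deviations and CAL. That does not follow. They have no CAL outcome to contribute, and selection on checklist values alone mainly narrows the range and costs precision. Counting them as non-leakers with poor values could itself weaken the association.

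The matter cannot simply be left to an analysis plan. Section 5.3 fixes who may leave the study, and later analysis cannot count patients whose records were not kept.

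**Conclusion.** The point holds in a limited form. The discretionary rule in section 5.3 hides any diversion away from anastomosis, so a lower CAL rate in the monitored period could reflect selection without anyone being able to see it. This bears on secondary objective 4 and the zero-group hypothesis. It creates no false reduction in the primary risk-factor question, where the loss is mainly of range and precision.

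The size is unknown. At an 8% baseline, the assumed 5% to 10% diverted at 15% to 20% risk gives an apparent relative fall of about 5% to 17%. The fall is smaller at a 13% baseline and is zero if diversion is unrelated to risk or equally common and equally selective in both periods. The protocol does not support saying that the withdrawn patients are the highest-risk ones or that leakage will fall. Separately, the two sentences of section 5.3 conflict: one confines withdrawal to participants' decisions before surgery, while the other permits it after an event during surgery.

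**What to change.** Replace the discretionary withdrawal in section 5.3 with one uniform rule: every consented patient with a planned anastomosis stays on record in both the monitored and the unmonitored period. Record whether an anastomosis was made, together with whatever checklist values are available. Reconcile this rule with the sentence that limits withdrawal to before surgery.

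Keep CAL per constructed anastomosis as the leak rate. Report the no-anastomosis rate beside it, by monitored and unmonitored period. Give CAL per planned anastomosis only as a supporting rate, because it also falls with diversion, and by more.

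The cost is protocol wording and a few extra records. These are needed in the unmonitored period as well, since a count from one period alone allows no comparison. The rates must also be read together, which is less simple than a single figure. The change concerns records and reporting only and leaves the surgical decision untouched.
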